Weight based RBV, 600 mg to 1200 mg, will be dose-divided to twice daily. This dose is approved for treatment of adult and adolescent patients with chronic HCV infection in combination with pegIFN. The same dose is selected for this study because its safety profile has been well characterized when administered with pegIFN, including incidence of hemolytic anemia, and there are well-defined dose reduction criteria in the event of RBV-induced anemia as noted in Section 6.1.7.4. In addition, the RBV dose was studied in the absence of pegIFN in adults in Studies M12-267, M12-746, M12-998, M11-652, M11-646, M13-098, M13-389, M13-961, M14-002, and M14-004, and in adolescents in Study M14-748, and the RBV dose was found to be generally safe and well tolerated and resulted in high SVR rates. It has been demonstrated that for previous virologic failures, the inclusion of additional drugs that have different mechanisms of action in the combination retreatment regimen will increase the probability to achieve SVR.⁵⁰

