- Post-nadir (preceding value is lower than the subsequent value)
ALT > 5 × ULN (regardless of grade change);
- Total bilirubin ≥ 2 × ULN and > baseline (i.e., a post-baseline value must be more extreme than the baseline value to be considered);
- Post-nadir ALT > 3 × ULN and total bilirubin > 2 × ULN;
- Post-nadir ALT > 3 × ULN and total bilirubin ≤ 2 × ULN.

Four listings (one for each bullet above) of all hepatic laboratory values including ALT, AST, total, indirect and direct bilirubin, ratio of direct to total bilirubin, and alkaline phosphatase values will be provided for each subject who met the criterion defined above.

Hepatic Laboratory Abnormalities of Interest

Among the events assessed under "Assessment of Hepatic Laboratory Values," the following criteria are of interest:

- Confirmed post-nadir ALT > 5 × ULN;
- Post-nadir ALT > 3 × ULN and a concurrent total bilirubin > 2 × ULN with a direct/total bilirubin ratio > 0.4.

To support the assessment of hepatic laboratory abnormalities of interest, the following potential events will be summarized:

- Confirmed post-nadir $ALT > 5 \times ULN$;
- Post-nadir $ALT > 3 \times ULN$ and total bilirubin $> 2 \times ULN$ and direct/total bilirubin ratio > 0.4 .

Two listings (one for each bullet) of all hepatic laboratory values including ALT, AST, total, indirect and direct bilirubin, ratio of direct to total bilirubin, and alkaline phosphatase values will be provided for each subject who met the criterion defined above.

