For the **assessments of hepatic laboratory values** and **hepatic laboratory abnormalities of potential interest**, the maximum ratio relative to the ULN will be used to determine if subjects meet any of the criteria listed above. The ALT and total bilirubin values do not need to be concurrent in order to meet the defined criteria in statistical summaries. For ALT, the post-baseline value must represent an increase from the first nadir (including baseline) to be counted. First nadir is defined as the last value prior to the first increase. For total bilirubin, a subject will be counted if the post-baseline laboratory value meets the above criteria regardless of the baseline laboratory value (i.e., the post-baseline laboratory value does not need to be worse than the baseline laboratory value), except where noted above. A confirmed post-nadir increase in ALT is defined as two consecutive values of $ALT > 5 \times ULN$ after nadir, either both during treatment or at the final treatment measurement and the next consecutive post-treatment measurement. A single post-nadir ALT value of greater than $5 \times ULN$ followed by lost to follow-up (no additional ALT values) also will be considered (i.e., will not require confirmation). The ratio of direct to total bilirubin will be calculated using the same date/time sample corresponding to the total bilirubin elevation.

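### SAP 11.4.2 does not say which elevated bilirubin sample supplies the direct/total ratio; if it is the maximum, the supporting liver screen can omit a subject who meets the criterion of interest

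*SAP*

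**What the plan says.** SAP 11.4.2 sets out three related items.

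- **The abnormality of interest**, under Hepatic Laboratory Abnormalities of Interest: "Post-nadir ALT > 3 × ULN and a concurrent total bilirubin > 2 × ULN with a direct/total bilirubin ratio > 0.4". ALT and bilirubin are concurrent here.
- **A supporting summary**, introduced by "To support the assessment of hepatic laboratory abnormalities of interest, the following potential events will be summarized". It uses the same three thresholds without the word concurrent and has its own listing.
- **A broader criterion**, under Assessment of Hepatic Laboratory Values: "Post-nadir ALT > 3 × ULN and total bilirubin > 2 × ULN", with no ratio condition. Its listing shows all hepatic values, including direct bilirubin and the direct/total ratio.

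The derivation rules at the end of the section cover the hepatic assessments and the potential events. They say that "the maximum ratio relative to the ULN will be used to determine if subjects meet any of the criteria listed above", that "The ALT and total bilirubin values do not need to be concurrent in order to meet the defined criteria in statistical summaries", and that "The ratio of direct to total bilirubin will be calculated using the same date/time sample corresponding to the total bilirubin elevation". No rule covers a subject with more than one sample above 2 × ULN.

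All subjects are assigned ribavirin. Bilirubin is scheduled on treatment at Weeks 2, 4, 8 and 12, and also at Week 16 in Arm B (SAP 4.2; Protocol Appendix C), so several elevated values per subject are possible.

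**The concern.** A maximum is enough for a threshold on a single variable: if any value crosses the line, the largest one does. It is not enough for a joint condition on total bilirubin and the direct fraction, because the fraction need not be highest when the total is highest. If one bilirubin sample per subject is tested and that sample is the peak, a later sample that meets every part of the condition is never examined.

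The summary is meant as a screen for potential events supporting the concurrent criterion, and dropping concurrency makes it broader. A screen of that kind should contain every subject who meets the target definition.

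The population makes the pattern plausible. Protocol 5.6.4.1 describes ribavirin's safety profile as "including incidence of hemolytic anemia", and Protocol 6.1.7.4 treats falls in hemoglobin as a well-known effect of the drug. Subjects with compensated cirrhosis are enrolled. At stake is the count for the only threshold criterion in the SAP that uses the direct fraction. Two programmers could also read the text differently and report different counts.

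**Working it through.** The SAP states no figure on this point, so there is nothing to reproduce. The check applies the rule as written to small assumed records.

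**Notation.** For on-treatment post-baseline sample j, B(j) is total bilirubin in multiples of ULN, R(j) is the direct/total ratio, and ALT(j) is ALT in multiples of ULN. A is the largest ALT after the first nadir, defined in the SAP as the last value before the first increase.

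- *Target (abnormality of interest):* some post-nadir sample j has ALT(j) > 3, B(j) > 2 and R(j) > 0.4.
- *Reading 1 (ratio at the maximum):* A > 3, B(m) > 2 and R(m) > 0.4, where m is the sample with the largest B.
- *Reading 2 (ratio at any elevated sample):* A > 3, and some sample j has B(j) > 2 and R(j) > 0.4.
- *Broader criterion:* A > 3 and B(m) > 2.

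A subject who meets the target always meets Reading 2 and the broader criterion. The same subject need not meet Reading 1.

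**Assumed records.** All four share baseline ALT 1.5, bilirubin 0.8 and ratio 0.30; ALT 0.9 at Week 2, 0.7 at Week 4, 3.6 at Week 8 and 2.0 at Week 12; and ratios of 0.15, 0.18, 0.55 and 0.50 at Weeks 2, 4, 8 and 12. The first nadir is Week 4, so A = 3.6. Bilirubin at Week 4 is 2.0 (1.5 in subject 2) and at Week 12 is 1.5. Only Weeks 2 and 8 decide the result:

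| Subject | B, Week 2 | B, Week 8 | Target met | Reading 1 | Reading 2 | Broader criterion |
|---|---|---|---|---|---|---|
| 1 | 2.6 | 2.3 | Yes | **No** | Yes | Yes |
| 2 | 1.8 | 2.3 | Yes | Yes | Yes | Yes |
| 3 | 2.6 | 3.1 | Yes | Yes | Yes | Yes |
| 4 | 2.6 | 1.7 | No | No | No | Yes |

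Subject 1 is the problem case. Week 8 has ALT 3.6, bilirubin 2.3 and ratio 0.55, which is the abnormality of interest with ALT and bilirubin in the same sample. Reading 1 looks only at Week 2, finds a ratio of 0.15, and does not count the subject.

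**When masking occurs.** It requires 2 < B(later) < B(peak) and R(peak) ≤ 0.4. Subjects 2 to 4 show that it disappears when the earlier peak is lower than the later value, or when the later value is not above 2 × ULN.

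**Size of one omission.** With 50 planned subjects, 1/50 = 2.0% becomes 0/50 = 0%. The Wilson 95% limits are [p + z²/2n ± z√(p(1−p)/n + z²/4n²)] / (1 + z²/n), with z = 1.96 and n = 50:

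- 1/50: (0.0584 ± 0.0546) / 1.0768 = 0.4% to 10.5%.
- 0/50: upper limit z²/(n + z²) = 3.84/53.84 = 7.1%.

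These are the complements of the N = 50 rows in SAP Table 3 (89.5% to 99.6%, and 92.9% to 100%). The SAP plans no interval for this count; the limits only show scale.

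**The case against.** The strongest reply is that the SAP never places the ratio at the maximum. The sentence on the maximum concerns multiples of ULN, and a direct/total ratio is not one. The sentence on the ratio refers to the bilirubin elevation, which could mean any sample above 2 × ULN. This stands in part: the text is ambiguous, and one reading does no harm. But the maximum is said to decide any of the listed criteria and the elevation is in the singular, so Reading 1 is the more natural one. Nothing in the section selects Reading 2.

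A second reply is that the case is not lost. This stands. A masked subject necessarily meets the broader criterion, is counted there, and is listed with every direct bilirubin value and ratio. The listing for increases to Grade 2 or higher may show the subject again. With about 50 subjects these listings can be read by hand. What remains wrong is the dedicated count and its listing, and the SAP prescribes no sample-by-sample ratio check elsewhere.

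A reader might also infer that the rule can only miss cases. Against the concurrent criterion that does not follow: because ALT and bilirubin need not coincide in the summaries, the screen can also count subjects who never met the target in one sample. The error runs one way only when Reading 1 is compared with Reading 2.

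Finally, a reader might infer that ribavirin hemolysis makes masking common. The documents name hemolytic anemia but give no size, timing, fraction or frequency for a bilirubin peak. An early, mainly indirect peak is an inference, and any masking percentage would come from assumed distributions.

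**Conclusion.** The point holds as a defect in a derivation rule. On its natural reading, SAP 11.4.2 lets the potential-events summary and its listing omit a subject who meets the concurrent criterion of interest. On the alternative reading there is no omission, but the text does not settle which applies.

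The consequence is limited. Masking needs a specific sequence, the subject remains visible under the broader criterion, and the study is descriptive with no hypothesis test, so no efficacy result is touched. The number of affected subjects cannot be estimated and may be zero. The result rests on reading the two derivation sentences together; the records in the check are assumed and show only that the omission is possible. The change is still worth making, because a safety count could read zero when the collected data contain an event.

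**What to change.** In SAP 11.4.2, state that the direct/total ratio is evaluated at every on-treatment post-baseline sample with total bilirubin above 2 × ULN. The potential-event criterion is met if any such sample has a ratio above 0.4, together with a post-nadir ALT above 3 × ULN. Keep the maximum-value rule for the hepatic criteria that do not use the ratio. The allowance for non-concurrent ALT and bilirubin in the summary can stay as it is.

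The cost is one sentence and a small programming change. It uses data already collected and alters no clinical management rule. If the sponsor already intended Reading 2, this only clarifies the text; if it intended the maximum, it corrects the count.

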11.5 Analysis of Vital Signs Data

11.5.1 Variables and Criteria Defining Abnormality

Vital sign variables are body temperature, sitting systolic blood pressure, sitting diastolic blood pressure, sitting pulse rate, and body weight.

The criteria for Potentially Clinically Significant (PCS) vital sign findings are presented in [Table 12](#).

Table 12. Criteria for Potentially Clinically Significant Vital Sign Values

Test/Measurement	Very Low (VL)	Very High (VH)
Systolic Blood Pressure	≤ 90 mmHg AND A decrease of ≥ 20 mmHg from baseline	≥ 180 mmHg AND An increase of ≥ 20 mmHg from baseline
Diastolic Blood Pressure	≤ 50 mmHg AND A decrease of ≥ 15 mmHg from baseline	≥ 105 mmHg AND An increase of ≥ 15 mmHg from baseline
Pulse Rate	≤ 50 bpm AND A decrease of ≥ 15 bpm from baseline	≥ 120 bpm AND An increase of ≥ 15 bpm from baseline
Weight	A decrease of $\geq 15\%$ from baseline	An increase of $\geq 15\%$ from baseline
Body Temperature		$> 38.3^\circ\text{C}$ AND An increase of $\geq 1.1^\circ\text{C}$ from baseline

11.5.2 Statistical Methods

The baseline value for vital signs will be the last measurement on or before the day of the first dose of study drug. The same baseline value will be used for change to Treatment Period visits and change to Post-Treatment Period visits.

For each vital sign parameter listed in Section 11.5.1, values at each visit (baseline and post-baseline, including applicable post-treatment visits) will be summarized with the sample size, mean, standard deviation, minimum, median, and maximum.

The number and percentage of subjects with on-treatment values meeting the specified criteria for PCS vital sign values ([Table 12](#)) will be summarized. A post-baseline value must be more extreme than the baseline value to be considered a PCS finding. A separate

listing will be provided that presents all vital sign values for the subjects meeting PCS criteria during treatment.

11.6 Analysis of HIV-1 RNA and Flow Cytometry

If this study enrolls HCV/HIV co-infected subjects, plasma HIV-1 RNA and flow cytometry data will be presented in subject data listings.

12.0 Summary of Changes

12.1 Summary of Changes Between the Latest Version of the Protocol and SAP

1. The planned analyses (Section 4.4) have been updated for better clarity.
2. The category cutoffs of baseline HCV RNA level have been changed (Section 7.1 and Section 10.6) to reflect current HCV project standards.
3. Certain efficacy subgroup variables have been changed (Section 10.6) because of the small sample size of the study and the current HCV project standards.
4. The resistance analyses (Section 10.8) have been updated to reflect current HCV project standards.
5. Analyses for HCV/HIV co-infected subjects (Section 7.3, Section 10.8.2, Section 11.3) have been deleted because of the anticipated small sample size of the HIV-1 co-infected subjects; subject-level data will be presented in listings.
6. For subgroups of treatment experience prior to enrolling in the AbbVie HCV parent study, "treatment-naïve" and "treatment-experience, DAA-naïve" are combined as "treatment-naïve/DAA-naïve" (Section 7.1 and Section 10.6) because of the small sample size of the study and because the recommended regimens of ABT-493/ABT-530 are the same for treatment-naïve and DAA-naïve GT1, 2, 4, 5, 6 subjects.

7. The percentage of subjects with virologic failure through Post-Treatment Week 24 has been added to additional efficacy analyses (Section 10.7) to reflect current HCV project standards.
8. Safety analyses will only be performed for the overall population (Section 11.1) because of the small sample size of the study and the current HCV project standards.
9. Analyses for vital signs have been updated (Section 11.5.2) according to the current HCV project standards.

